17.2.4 Safety Endpoints

Safety endpoints include all adverse events related and unrelated to the study treatment.

17.3 Statistical Hypothesis

In this study, we will test the following hypotheses:

• $H_0: P_{a1}-P_{s1}=0$

• $H_1: P_{a1}-P_{s1}\neq 0$

Where P_{a1} is the CSBM1 success rate in the active arm, and P_{s1} , the CSBM1 success rate in the placebo arm. AND:

 $\bullet \quad H_0: P_{a2}\text{-}P_{s2}\!\!=\!\!0$

• $H_1: P_{a2}-P_{s2}\neq 0$

Where P_{a2} is the CSBM2 success rate in the active arm, and P_{s2}, the CSBM2 success rate in the placebo arm

17.4 Sample size

A sample size is calculated to test the null hypotheses. Calculations (using SAS® proc power) show that a sample size of 92 subjects (46 in each study arm), would provide 80% power at a study wise 5% level of significance (two-sided), i.e., 2.5% for each one of the primary endpoints to detect a difference of 28% in the success rate, assuming a success rate of 12% in the placebo arm.

The sample size will be increased to at least 102 subjects (51 in each study arm) to account for a potential 10% of drop-out rate.

Doc No: 280CLD

Rev: 01 Date: 24 May 2021

Page 68 of 103

17.5 Interim Analyses

One interim analysis will be performed, after about 80 evaluable subjects will complete 8 weeks of treatment. Planning an interim analysis that permits an increase in the sample size as described below does not additionally inflate the type I error according to references 25-27. In addition, the final analysis is performed using the conventional test as appropriate for the statistical hypothesis. ONLY the un-blinded statistician and members of the DSMB committee will be exposed to the report. Investigators and company directors will only be informed of a decision to continue or to discontinue the trial, or to implement modifications in sample size increase.

17.5.1 Procedure

After all the relevant data will be entered into the database, and the database cleaned, a soft lock to the database will be performed. An independent un-blinded statistician (not the study statistician) will perform the assessments described below. At the interim analysis, the data of the evaluable subjects will be analyzed.

17.5.2 Blinding

ONLY the un-blinded statistician will be exposed to the subjects' treatment allocation. Investigators and company directors will only be exposed to the interim report.

The members of the DSMB (Data and Safety Monitoring Committee) may also have access to the unmasked information of the interim analysis. Investigators and company directors will only be informed of a decision to continue or to discontinue the trial, or to implement modifications in sample size of the trial. The un-blinded statistician who is responsible for conducting the interim analyses should ensure that the unmasked data is not available to any unauthorized person within or outside the company.

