15.9 Baseline / randomization visit (day 0)

After the run-in period, if subject is found eligibile for randomization, the Sponsor will send eligibility confirmation to the site study team following which the subject will be invited to the medical center for the baseline visit for further assessment. Eligibility will be reassessed, making sure there were not any relevant changes since the screening visit.

Eligible subjects will be randomized to either Vibrant or Placebo arm (1:1ratio), for a treatment period of 8 weeks.

The subjects will be trained in the medical center how to use the base unit. He/she will activate the first capsule and will ingest it in front of the medical staff. All other capsules will be ingested at the subject home.

During the 8 weeks treatment period, subjects will ingest the capsules twice a week: one capsule on Mondays, and on Thursdays (total of 16 capsules for the whole study). Subjects will not ingest any capsule on any other days of the week.

If the visit falls on a day which is not Monday or Thursday, the subject should ingest the first capsule on site and as follow:

Doc No: 280CLD

Rev: 01 Date

Date: 24 May 2021

Page 52 of 103

In case baseline visit occurs on Tuesday, subject will swallow the 1st capsule at the site and the next capsule will be swallowed on Thursday

In case baseline visit occurs on Wednesday, subject will swallow the 1st capsule at the site and the next capsule will be swallowed on Monday

In case baseline visit occurs on Friday, subject will swallow the 1st capsule at the site and the next capsule will be swallowed on Monday

Actual point of enrollment for the subject is considered the day of first capsule intake.

The first 2 weeks of treatment will be considered as a subjects' training period.

During the visit, an interview will be conducted, where the following topics will be discussed: compliance to filling in the daily information on the eDiary, change in concomitant medication/rescue taken, evolution of constipation symptoms, subject's perceptions about the treatment, motivation of the subject, refreshing the definitions of what is "complete" evacuation and digital maneuver or any other relevant topic. In addition, the subject will receive capsules supply for Treatment period 1 (period of 4 weeks between baseline and next visit).

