15.19 Deviations from study protocol

Any deviation from the study protocol should be notified to the sponsor, documented on study deviation forms and reported to the Ethics Committee as required.

Protocol deviations related to treatment compliance missed capsule, capsule taken on a non-capsule administration day, etc.) will not be declared on the protocol deviation form accessible via the **EDC** (Electronic Data Capture). Protocol deviations related to treatment compliance will be

monitored and declared by the Sponsor, CRO and sites using a platform external to the EDC. This external platform will use the information transmitted from the base units about activations (base unit serial number, date and time of activation, success/failure) as a basis to monitor treatment compliance.

Additional information transmitted by the subject from the eDiary about number of capsules taken out of the blister and swallowed for each day, as well as direct information given by the subject to the study coordinator by phone, email or SMS, will be used by the Sponsor and CRO to make a final decision about treatment compliance, for each day of treatment, for all subjects.

A final list of protocol deviations related to treatment compliance will be issued at the end of the study, from the external platform, and signed by the site. This list will be considered equivalent as protocol deviations forms. The site will not manually enter these protocol deviations in the EDC.

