17.5.3 Decision Rules

The purposes of the interim analysis is to re-assess the sample size based on conditional power

The study will either continue to the originally planned sample size if the result is "favorable", stop for futility if the result is "unfavorable", or an increase will be made to the sample size if the result is "promising". These decisions will be made based on the

Page 69 of 103

conditional power (CP), defined as the conditional probability that the result will exceed a critical value at the interim given the observed effect size $\widehat{\delta_1}$ = difference between CSBM success rates active versus placebo at the interim look. Notation:

n1= sample size at interim analysis (40 subjects in each study arm).

n2= original sample size calculated based on assumed effect size (92).

nmax = the highest sample size the company is willing to use, <math>nmax = 250 (including allowance for drop-out).

CPmin=is the calculated minimum CP based on the ratios nmax/n2, n1/n2 and the target study power (80%).

The following are the decision rules for the interim analysis. These depend on the zone into which CP falls at the interim, the calculated CPmin, the maximum sample size designated for the study and the % of the originally planned sample size at which the interim analysis will be performed. Following this principle does not inflate the Type I error.

- 1. If the respective conditional power for each of the primary endpoints is < 25.78or if the difference between the success rate (treatment –placebo) for both primary endpoints is less than 10%, then stop the trial for futility.
- 2. a. If the conditional power for both primary endpoints is 25.78≤ CP < 80% then recalculate the sample size to recover the targeted 80% for both endpoints, the maximum sample size selected will be the larger of the two.
 - b. If the CP of only one of the primary endpoints is $25.78 \le CP \le 80\%$ then recalculate the sample size to recover the targeted 80% for that endpoint alone.
 - In both cases a and b, the maximum sample size for the study will be 250 subjects
- 3. If the respective conditional power for each of the primary endpoints is $\geq 80\%$ then continue to the originally planned sample size. Note that the interim analysis will be conducted on both the ITT and mITT analysis sets, and the study will be stopped due to futility only if the interim effects in both populations fall below the threshold.

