28. SUBJECT / STUDY DISCONTINUATION

Page 81 of 103

Subjects should be removed from the study whenever considered necessary for their welfare or when the subject expresses a desire to withdraw from the study. Non-compliance with the protocol, the occurrence of a Serious Adverse Event or any medical condition that, in the opinion of the investigator, warrants discontinuation from the study for the safety of the subject, may necessitate discontinuing a subject. If a subject is discontinued, the reason must be entered on the case report form and signed by the investigator. In case of any questionable situation, the study monitor or Vibrant Ltd. personnel should be consulted. When a subject is removed from the study as a result of Serious Adverse Event, a final physical examination must be performed. Subjects removed from the study because of an adverse event will be followed-up until the adverse event has been resolved.

In the case that the occurrence of adverse events is greater than anticipated, the clinical investigation will be suspended; in such a case, a safety committee will be arranged to decide if the study could be continued. The Ethics Committee will be notified and the results of the safety committee discussions will be brought for the EC/IRB review and decision.

Early termination could be a result of:

- 1. Withdrawal of informed consent by the subject.
- 2. Subjects who after inclusion develop medical diseases which may affect the function and interpretation of study results.
- 3. Serious protocol deviation.
- 4. Non-compliance with medical device administration or study procedures as determined by the sponsor.
- 5. Change in subject's condition.
- 6. Subject is Lost to follow-up.
- 7. Confirmed pregnancy.
- 8. Regulatory authorities stop the trial.

During the study, subjects exiting the trial will be replaced with new subjects, up to 10%

Site staff should set an early termination visit as soon as they become aware of subject's discontinuation. During this visit, any remaining study supplies should be collected and accountability should be conducted if applicable. 'End of study' from should be completed in source documents and any other relevant information should be documented (for example, in case of AE).

Doc No: 280CLD

Rev: 01 Date: 24 May 2021

Page 82 of 103

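### One sentence in 17.5.2 gives investigators and company directors the interim report, contradicting the decision-only rule stated in 17.5 and again later in 17.5.2

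*Combined protocol and SAP*

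**What the plan says.** Three places in the combined protocol and SAP state who learns what from the interim analysis.

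- Section 17.5 (Interim Analyses): "ONLY the un-blinded statistician and members of the DSMB committee will be exposed to the report". It adds that investigators and company directors hear only the decision.
- Section 17.5.2 (Blinding), first paragraph: subject-level allocation is kept to the un-blinded statistician, and then "Investigators and company directors will only be exposed to the interim report".
- Section 17.5.2, second paragraph: "The members of the DSMB (Data and Safety Monitoring Committee) may also have access to the unmasked information of the interim analysis", followed by "Investigators and company directors will only be informed of a decision to continue or to discontinue the trial" or to change its sample size. The paragraph ends by making the un-blinded statistician responsible for keeping unmasked data from anyone not authorized, inside or outside the company.

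Section 17.5.1 adds that this statistician is independent and is not the study statistician. Section 17.5.3 bases the decision on conditional power, computed from the observed "difference between CSBM success rates active versus placebo at the interim look".

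**The concern.** The same two groups are excluded from the report in 17.5, given it in 17.5.2, and limited to the decision one paragraph later. The conflicting sentence is in the section titled Blinding, where site and sponsor staff would look for the access rule. It is an operative instruction in the current text, not background.

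What is at stake is the conduct of the trial after the interim look. The trial may go on to its planned size or be enlarged to as many as 250 subjects, and the primary endpoints rest on subjects' own reports of complete evacuation. Investigators assess subjects and discuss symptoms and motivation with them at visits. The sponsor also acts at subject level. Under 15.9, "the Sponsor will send eligibility confirmation to the site study team". Under 15.19, diary and contact information "will be used by the Sponsor and CRO to make a final decision about treatment compliance, for each day of treatment, for all subjects". Section 28 lists among the reasons for early termination "Non-compliance with medical device administration or study procedures as determined by the sponsor". A decision-only rule exists so that people in such positions do not work with knowledge of the emerging treatment comparison.

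**Working it through.** No figure in the plan bears on this point, so no arithmetic applies. The check sets the passages side by side.

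**Step 1: who receives what.**

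| Place | Report or unmasked results | Investigators and company directors |
|---|---|---|
| 17.5 | Report: un-blinded statistician and DSMB only | Decision only |
| 17.5.2, first paragraph | Allocation: un-blinded statistician only | The interim report |
| 17.5.2, second paragraph | Unmasked interim information: DSMB may also have access | Decision only |

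**Step 2: can all three be followed?** If investigators and company directors receive the report, 17.5 is breached and so is the second paragraph of 17.5.2. If they do not receive it, the sentence in the first paragraph is not followed. No course of action meets all three.

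**Step 3: does a milder reading reconcile them?** Two are available.

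- The sentence may be meant as a limit: the report, but not individual allocation. Section 17.5 still closes the report itself to these groups, and the second paragraph of 17.5.2 still allows only the decision.
- The sentence may refer to a separate, blinded report. Sections 17.5 to 17.5.4 define no such document.

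Neither reading removes the conflict.

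**Step 4: what could the report show?** The 17.5.3 rules need the between-arm difference in success rates and the conditional power for each primary endpoint. The trial stops for futility if conditional power falls below 25.78 for each endpoint, or if the difference is under 10% for both. A report of that assessment would naturally contain comparative results. The plan does not specify the report's contents, so this is an inference.

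**Step 5: what would stay protected?** Individual allocation is not released by this sentence, and subjects stay blinded. The exposure is to the aggregate comparison, not to any one subject's arm.

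**The case against.** The strongest reply is that the intended rule is plain. Decision-only access is stated twice, the un-blinded statistician is independent, and that person has an explicit duty to withhold unmasked data. Harm needs two further things: that the stray sentence is followed over two contrary statements, and that the report shows results by arm. Even correct operation tells the sponsor something, because an announced increase points to a conditional-power zone under 17.5.3.

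This stands as far as it goes. It makes the sentence a probable drafting error and lowers the likelihood of harm. It does not remove the contradiction, and the duty to exclude unauthorized people depends on a clear statement of who is authorized.

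A reader might infer more than the documents support:

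- **That the plan intends to unblind the sponsor, or that the result would be biased or the type I error inflated.** Two of the three statements say the opposite of the first, and nothing in the documents demonstrates bias or inflation.
- **That company directors would use interim results in subject-level decisions.** Sections 15.9, 15.19 and 28 name the sponsor, not company directors, and the link is not documented. Eligibility confirmation comes before randomization, so it cannot act by arm. Compliance decisions start from base-unit activation data.
- **That the allocation sentence in 17.5.2 contradicts DSMB access.** The DSMB sentence extends the one before it by saying members may also have access, and it concerns interim information, which may be summaries by arm. The two can be read together.
- **That section 18 permits unblinded efficacy looks.** Its general provision for halting the study mentions unsatisfactory efficacy endpoints, but does not say that any such review is by arm.

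**Conclusion.** The point holds as an internal inconsistency in an operative blinding rule. One sentence in 17.5.2 conflicts with 17.5 and with the paragraph that follows it. The text alone establishes this with high confidence.

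The consequence is conditional: the sentence would have to be followed, and the report would have to contain the between-arm results on which 17.5.3 relies. In that case people running the trial could see comparative results while enrolment may continue up to 250. The size of any effect on the trial cannot be derived from the documents, and no range is offered. The correction is worth making before an interim report is produced, because it protects a double-blind comparison at almost no cost.

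**What to change.** Delete from the first paragraph of 17.5.2 the sentence that gives investigators and company directors the interim report. If a replacement is wanted, repeat the 17.5 rule: only the un-blinded statistician and DSMB members see the interim report, and investigators and company directors receive the decision only.

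Leave unchanged the sentence on subject-level allocation and the one saying that the DSMB may also have access. The first does not concern the report, and adding the DSMB to it would grant subject-level allocation that 17.5 does not give. Section 18 needs no change for this purpose.

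The cost is a short protocol amendment with EC/IRB re-approval under section 21, for a trial planned in about 30 centers. No extra subjects or procedures are needed, and the decision thresholds are untouched.

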17.5.3 Decision Rules

The purposes of the interim analysis is to re-assess the sample size based on conditional power

The study will either continue to the originally planned sample size if the result is "favorable", stop for futility if the result is "unfavorable", or an increase will be made to the sample size if the result is "promising". These decisions will be made based on the

Page 69 of 103

conditional power (CP), defined as the conditional probability that the result will exceed a critical value at the interim given the observed effect size $\widehat{\delta_1}$ = difference between CSBM success rates active versus placebo at the interim look. Notation:

n1= sample size at interim analysis (40 subjects in each study arm).

n2= original sample size calculated based on assumed effect size (92).

nmax = the highest sample size the company is willing to use, <math>nmax = 250 (including allowance for drop-out).

CPmin=is the calculated minimum CP based on the ratios nmax/n2, n1/n2 and the target study power (80%).

The following are the decision rules for the interim analysis. These depend on the zone into which CP falls at the interim, the calculated CPmin, the maximum sample size designated for the study and the % of the originally planned sample size at which the interim analysis will be performed. Following this principle does not inflate the Type I error.

- 1. If the respective conditional power for each of the primary endpoints is < 25.78or if the difference between the success rate (treatment –placebo) for both primary endpoints is less than 10%, then stop the trial for futility.
- 2. a. If the conditional power for both primary endpoints is 25.78≤ CP < 80% then recalculate the sample size to recover the targeted 80% for both endpoints, the maximum sample size selected will be the larger of the two.
 - b. If the CP of only one of the primary endpoints is $25.78 \le CP \le 80\%$ then recalculate the sample size to recover the targeted 80% for that endpoint alone.
 - In both cases a and b, the maximum sample size for the study will be 250 subjects
- 3. If the respective conditional power for each of the primary endpoints is $\geq 80\%$ then continue to the originally planned sample size. Note that the interim analysis will be conducted on both the ITT and mITT analysis sets, and the study will be stopped due to futility only if the interim effects in both populations fall below the threshold.

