17.5.4 Controlling the Alpha level for the primary endpoint

The overall alpha level for this study is 5%. According to references 25-27, planning an interim analysis that permits an increase in the sample size as described above does not inflate the type I error.

Doc No: 280CLD	
Rev: 01	Date: 24 May 2021
Page 70 of 103	

Page 70 of 103

Randomization 17.6

After a subject meets the eligibility criteria, he/she will be equally allocated (with a 1:1 ratio) to one of the following treatment groups based on a randomization scheme with randomized blocks' size stratified by center:

- Vibrant capsule administered twice a week
- Placebo capsule administered twice a week

The randomization scheme will be prepared by BioStats using the SAS® (version 9.4.) random number generating procedure.

17.7 **Blinding**

This is a double-blind study. The subjects and evaluators will be blinded to the treatment allocated to each subject.

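### Section 17.5.3: the 25.78% limit is not the CPmin of the plan's own re-estimation rule; the matching bound is 28.6% at two-sided 5%, or 27.65% at 2.5% per endpoint

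*Combined protocol and SAP*

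**What the plan says.** Section 17.5.3 gives the inputs: "n1= sample size at interim analysis (40 subjects in each study arm"), "n2= original sample size calculated based on assumed effect size (92") and "nmax = 250 (including allowance for drop-out"). CPmin is described as "CPmin=is the calculated minimum CP based on the ratios nmax/n2, n1/n2 and the target study power (80"%).

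The resulting number enters the futility rule ("If the respective conditional power for each of the primary endpoints is < 25.78or if the difference" in success rates is under 10 points) and the lower edge of the zone in which N may grow. Inside that zone, rule 2 tells the statistician to "recalculate the sample size to recover the targeted 80% for both endpoints" (or for the single endpoint concerned), with 250 only as a ceiling.

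Section 17.5 keeps the conventional final test. Section 17.5.4 states that "planning an interim analysis that permits an increase in the sample size as described above does not inflate the type I error", and 17.5.3 and 17.9.2.1 say the same in substance. The plan does not state the critical value used for conditional power: the overall level is two-sided 5% (17.9.2.1), while the sample size uses 2.5% per primary endpoint (17.4).

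**The concern.** In a promising-zone design, CPmin is the lowest interim conditional power at which enlarging the trial, and still using the conventional test, leaves the conditional type I error no larger than at the original size. It therefore depends on what N becomes at that point. A rule that jumps to the maximum and a rule that stops at 80% conditional power have different bounds. The plan names the 80% target as an input to CPmin and applies a recover-to-80% rule, so its figure should be the bound for that rule.

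At stake is a constant that decides between stopping and enlarging, and on which the plan's reasoning for an unadjusted final test leans.

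**Working it through.** **Inputs.** n1 = 80 (2 × 40), n2 = 92, nmax = 250 and target 80%, all from 17.5.3. Conditional power (CP) uses the observed interim effect, as 17.5.3 specifies. Critical value zc = 1.960 (two-sided 5%) or 2.241 (two-sided 2.5%).

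**Formulas**, for interim statistic z1 and final size N:
- Conditional error: CE(z1, N) = 1 − Φ[(zc√N − z1√n1)/√(N − n1)]
- Conditional power: CP(z1, N) = 1 − Φ[(zc√N − z1√n1)/√(N − n1) − z1√(N − n1)/√n1]
- CPmin = CP(z1, n2) at the smallest z1 for which CE(z1, new N) ≤ CE(z1, n2).

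**Step 1: reproduce 25.78%.** Take zc = 1.960 and new N = 250. The condition is met with equality at z1 = 1.6087:
- N = 92: (18.799 − 14.389)/3.464 = 1.273, so CE = 0.1015. CP = 1 − Φ(1.273 − 0.623) = 0.2578.
- N = 250: (30.990 − 14.389)/13.038 = 1.273, so CE = 0.1015. CP = 1 − Φ(1.273 − 2.345) = 0.858.

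The plan's figure is matched. At that point N = 250 gives 85.8% conditional power, so the 80% target did not determine it. The same 25.78% results for any target of about 86% or more, because the cap then binds; its origin may be a wrong target rather than a deliberate jump rule.

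**Step 2: apply rule 2 at the same point.** At z1 = 1.6087 the N that recovers 80% is 213 evaluable (213/0.9 ≈ 237 with 10% drop-out), below the cap:
- CP: (28.605 − 14.389)/11.533 = 1.233; 1 − Φ(1.233 − 2.074) = 0.800.
- CE = 1 − Φ(1.233) = 0.1088, against 0.1015 at N = 92.
- Critical value that would preserve the conditional error: [√(133/12) × 4.411 + 14.389]/√213 = 1.992, above 1.960.

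The condition that defines CPmin therefore fails at the plan's threshold.

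**Step 3: bound under rule 2.** Solve CE(z1, N) = CE(z1, 92), with N set to recover 80%:

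| zc | z1 | N | CE at N and at 92 | CPmin | Jump to 250 instead |
|---|---|---|---|---|---|
| 1.960 | 1.637 | 204 | 0.1153 | 28.61% | 25.78% |
| 2.241 | 1.890 | 185 | 0.0925 | 27.65% | 22.86% |

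At zc = 2.241, CP = 25.78% corresponds to N of about 190, with CE 0.0886 against 0.0846 at 92. So 25.78% is too low under either level.

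**Step 4: units.** The ceiling is "250 (including allowance for drop-out"), while 80 and 92 count evaluable subjects. On the evaluable scale it is 250 × 0.9 = 225. A jump to 225 gives 27.19%, but the re-estimated bound is unchanged because N = 204 lies below either ceiling.

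**Step 5: size** (zc = 1.960, one endpoint).
- Chance of landing in the band: Φ(1.637) − Φ(1.609) = 0.003 under the null, and at most 2Φ(0.0144) − 1 = 0.011 under any effect.
- One-sided error: 0.025 + 0.00001 (band) − 0.00195 (rest of the enlargement zone) = 0.0231 with non-binding futility. With binding futility it is 0.0204.
- With 12% placebo success, the band is an interim difference of about 14 points, so the 10-point futility rule does not hide it.

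**The case against.** The strongest reply is that the plan's statement concerns overall type I error, and that survives. Control of the conditional error at every interim value is sufficient for overall control, not necessary. For one endpoint, correcting the bound changes the error by about 0.00001, and it is below 2.5% both before and after. This stands. A reader might infer from Step 2 that the trial's type I error is inflated, or that 17.5.4 is false on this account; the calculation does not support that.

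Three further objections have force.
- The critical value for CP is unstated, and the Benjamini-Hochberg procedure in 17.9.2.2 makes each endpoint's level depend on the other. It would be too strong to present 28.6% as the one correct number.
- Rule 2b enlarges the trial for one promising endpoint, and the other is then also tested at the larger N whatever its own CP. Correcting the threshold does not restore a pointwise guarantee.
- The interim data are coarse. With 40 per arm, only 4 of 41² = 1,681 outcome pairs fall in the band with a pooled-variance Z, and 6 with an unpooled one. At 12/40 against 6/40, CP is 25.6% pooled or 28.2% unpooled; one more active success makes it 51.3% pooled.

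These points limit the importance of the error. None makes 25.78% the bound for rule 2.

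**Conclusion.** The point holds as a mis-derived decision threshold. The 25.78% limit belongs to a jump to 250, not to the recover-to-80% rule that the plan states. It is 28.61 − 25.78 = 2.8 percentage points too low at two-sided 5%, and 27.65 − 25.78 = 1.9 points too low at 2.5% per endpoint.

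This rests on the normal approximation, current-trend CP, n1 = 80, n2 = 92 and the stated 80% target. The error-rate figures are for one endpoint at one-sided 2.5%. They make no claim about the two-endpoint family, and the rule 2b question remains separate and open. The mixed units are an inconsistency worth tidying, but they do not move the bound.

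**What to change.** In 17.5.3, state the critical value used for conditional power and, given the coarse data, the variance form of the interim Z. Replace 25.78% as the lower limit for increasing N with the matching value: 28.6% for z = 1.96 or 27.65% for z = 2.241. Have the unblinded statistician recompute it at the actual n1 by a pre-stated formula. List n1, n2 and nmax all as evaluable subjects (80, 92, 225) for consistency.

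The sponsor should also say what happens between the old and new limits. The futility limit can move up with the new bound, which keeps three zones. Alternatively it can stay at 25.78%, with the trial continuing to its planned size in between. The second option is not required, and it means finishing at 92 with roughly 26 to 29% conditional power.

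The cost is a few numbers and a sentence or two in one section, with endpoints, planned size and final test unchanged. About 1% of trials or fewer per endpoint would lose an enlargement. The treatment of the non-promising endpoint under rule 2b needs its own resolution.
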